9.1 Challenge Visits

A subset of subjects (N=40) will take part in activity and dietary challenges. Subjects will participate in challenges during any consecutive 2 days during Phase 2. Subjects should be in Automated Mode during this time. Subjects should engage in a minimum of 3 hours of activity per day. Activity in this age group could include examples such as playing, walking, hiking, running, gymnastics, kicking a ball, throwing a ball, or riding a bike or trike. Meal challenge will include under-bolusing for one meal per challenge day by reducing the number of carbohydrates for a given meal by 50%.

Subjects will be allocated to challenges based on investigator discretion until a subset of 40 subjects are reached.

Table 4: Challenges

Challenges	Day 1	Day 2
Meal: 50% reduction in carb entry into the bolus calculator for a given meal	X	X
Activity examples: Playing, walking, hiking, running, gymnastics, kicking a ball, throwing a ball, riding a bike or trike	X	X

Challenges will be conducted in an environment of the caregiver’s choosing and will not require a visit to the clinical study site. On the day of challenges, caregivers will be instructed to contact the clinical site on the agreed upon day to confirm the time of the activity and dietary challenges planned. At the conclusion of the activity, caregivers will contact the clinical site to provide the time the activity ended and provide a description of the activity and dietary challenges.

During the challenge visits, caregivers will be encouraged to:

- Follow their pre-exercise management such as insulin reduction for meal boluses, consumption of snacks, or adjust their insulin delivery settings.
- Treat themselves per their usual routine if they become hypoglycemic or hyperglycemic at any time during the exercise challenge.
- Obtain a fingerstick blood glucose value using the study dispensed BG meter if CGM is < 70 mg/dL or > 300 mg/dL.

During the challenges, clinical site staff will monitor the Horizon Data Portal. Subjects may participate in exercise if their CGM value is ≥70 mg/dL with the corresponding CGM trend either steady or increasing. Subjects will be discharged (meaning the site no longer has to actively monitor the HDP) from

each day of challenges when they meet the CGM criteria between 70-300 mg/dL on two consecutive checks for the last 30-minutes of their participation given that the CGM trend is not rapidly increasing or decreasing at these timepoints.

Investigator/site staff will conduct a telephone visit with the subject and caregiver within a few hours of the completion of each day of challenges to ensure the subject is safe.

Measuring Activity Levels and Carbohydrate intake

At Visit 2, Visit 9, Visit 11, and Visit 13, site staff will interview all subject caregivers to record the approximate amount of daily activity as well as daily carbohydrate intake with the addition of these questions:

1. Over the last week, how many hours on average does your child exercise per day? This may include activities such as playing, walking, hiking, running, gymnastics, kicking a ball, throwing a ball, riding a bike or trike.
2. Over the last week, what is the average daily carbohydrate consumption for your child?

9.2 Visit 4

Visit 4 represents the commencement of Phase 2 (hybrid closed-loop phase) and will be conducted in person at the clinical site on Study Day 1. All scheduled assessments will be performed according to Table 1: Schedule of Assessments for Phase 1 and Phase 2. This visit will include:

- Review of concomitant medications
- Average total daily insulin (approximately over the past 7 days)
- Average total daily basal insulin (approximately over the past 7 days)
- Average total daily bolus insulin (approximately over the past 7 days)
- Pump settings/MDI dosing
- Assessment of AEs
- Initiation of Horizon Data Portal monitoring
- Omnipod Horizon™ System device training conducted by trained clinical site staff
 - Subjects and/or parents/guardians will be trained on operating Omnipod Horizon™ in both Manual and Automated Modes.
 - This will include first time device set-up with entry of basal profile, bolus calculator settings with insulin:carbohydrate ratio, target glucose and correction factor.
 - The Pod will be filled with the subject's own U-100 rapid-acting insulin and placed on body. Subjects will also be trained on use of Dexcom G6 CGM, regardless of previous experience, setting up low (recommended to be 70 mg/dL or higher) and high glucose alerts (recommended to be 300 mg/dL or lower) and entering transmitter serial number into the Horizon App.
 - Subjects and/or parents/guardians may choose their desired target BG ranging between 110-150 mg/dL in increments of 10mg/dL, although the default and recommended setpoint is 120 mg/dL.

- In addition, Omnipod Horizon™ has a novel bolus calculator feature that incorporates both the CGM value and trend into the suggested bolus amount. In general, if the CGM values are trending up or down, the calculator will add or subtract insulin from the suggested bolus amount to help keep BGs within target range.
- Dispense Omnipod Horizon™ System
- Complaints/device deficiencies for CGM, BG and ketone meter
- Device uploads for CGM (via IQVIA), BG and ketone meter (not applicable if combining with Visit 2)
- Data review by clinician
- Removal of the subject's personal insulin pump (if applicable)
 - Investigators will use the Insulet-provided Patient Therapy Order Form (PTOF) as a guide to transition subjects from MDI to pump therapy (Appendix A)

If a subject is a current Dexcom G6 User and Visit 2 and Visit 4 occur on the same day, average total daily insulin and pump settings/MDI dosing only needs to be collected once.

At the conclusion of the training and completion of assessments, each subject's treatment will be initiated marking their commencement of the hybrid closed-loop phase.

9.3 Visit 5

Visit 5 will be conducted either over the telephone or in person at the clinical study site on Study Day 2 ± 1 day. This visit will include:

- Review of concomitant medications
- Assessment of AEs since last visit
- Complaints/device deficiencies such as occlusion alarms and system hazard alarms since last visit
- Device uploads for BG and ketone meter (if visit is conducted in person at the clinical study site)
- Data review of Automated Mode use by clinician

9.4 Visit 6

Visit 6 will be conducted either over the telephone or in person at the clinical study site on Study Day 3 ± 1 day, respectively. This visit will include:

- Review of concomitant medications
- Assessment of AEs since last visit
- Complaints/device deficiencies such as occlusion alarms and system hazard alarms since last visit
- Device uploads for BG and ketone meter (if visit is conducted in person at the clinical study site)
- Data review of Automated Mode use by clinician

9.5 Visit 7

Visit 7 will be conducted either over the telephone or in person at the clinical study site on Study Day 10 ± 3-days. This visit will include:

- Review of concomitant medications
- Assessment of vital signs (if visit is conducted in person at the clinical study site)
- Assessment of AEs since last visit
- Complaints/device deficiencies such as occlusion alarms and system hazard alarms since last visit
- Device uploads for BG and ketone meter (if visit is conducted in person at the clinical study site)
- Data review of Automated Mode use by clinician

9.6 Visit 8

Visit 8 will be conducted either over the telephone or in person at the clinical study site on Study Day 24 ± 3-days. This visit will include:

- Review of concomitant medications
- Assessment of AEs since last visit
- Complaints/device deficiencies such as occlusion alarms and system hazard alarms since last visit
- Device uploads for BG and ketone meter (if visit is conducted in person at the clinical study site)
- Data review of Automated Mode use by clinician

9.7 Visit 9

Visit 9 will be conducted either over the telephone or in person at the clinical study site on Study Day 38 ± 3-days. This visit will include:

- Review of concomitant medications
- Assessment of vital signs
- Assessment of AEs since last visit (if visit is conducted in person at the clinical site)
- Complaints/device deficiencies such as occlusion alarms and system hazard alarms since last visit
- Device uploads for BG and ketone meter (if visit is conducted in person at the clinical site)
- Data review of Automated Mode use by clinician
- Assessment of activity and routine carb consumption

9.8 Visits 10, 11 and 12

Visits 10, 11 and 12 will be conducted either over the telephone or in person at the clinical study site on Study Day 52 ± 3-days, 66 ± 3-days, and 80 ± 3-days. These visits will include:

- Review of concomitant medications

- Assessment of AEs since last visit
- Complaints/device deficiencies such as occlusion alarms and system hazard alarms since last visit
- Device uploads for BG and ketone meter (if visit is conducted in person at the clinical study site)
- Data review of Automated Mode use by clinician
- Assessment of activity and routine carb consumption (Visit 11 only)

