Abbreviations: S=Screening; ST1=Standard Therapy Day One; HCL=Hybrid Closed-loop; EW=Early Withdrawal; QC=Quality Control Testing; UV=Unscheduled Visit

^aEarly withdrawal visit will only be conducted for any subjects that started but did not complete the full study to include standard therapy and the hybrid closed-loop phase.

^bAll Screening and all ST1 assessments do not need to occur on the same day as long as the assessments occur within 30 days prior to the start of Phase 2/HCL Start/Study Day 1.

^cUnscheduled visits will serve as extra study visits, if needed.

^dIn the event of overlapping visit windows, no Phase 2 visits are to occur on the same date.

^eVisits identified as "T/O" can either be conducted in person at the clinical site or over the telephone. Visits identified as "O" can only be conducted in person at the clinical site. Vital signs, device uploads/data review from the BG and Ketone meter are not required at any visit conducted via telephone.

^fLab values obtained within six months prior to the screening visit may be used.

^gDocumentation only applicable if there are changes from previous assessment

^hStudy device training for the CGM, blood glucose and ketone meters

ⁱStudy device training for the Omnipod Horizon™ System

^jSubjects deemed exempt from wearing the study CGM for 14-days will be eligible to immediately commence the hybrid closed-loop phase at Visit 4 and may skip Visit 3 (Visit 1, Visit 2 and/or Visit 4 may all occur on the same day). For all subjects, any assessment required at more than one visit will only need to be completed once if the visits are done on the same day.

^kDevices will be returned to the site at the end of the subject's participation if the subject is not participating in the extension phase.

Table 2: Questionnaires

Visit	Caregiver of Subject*
Screening (Visit 1)	Clarke Questionnaire
Visit 2	WHO-5 DTSQs Parent P-PAID-Child Hypoglycemia Confidence Scale PSQI IDSS (T1) SUS
End of Phase 2 (~13 weeks) or Early Withdrawal	WHO-5 DTSQc Parent P-PAID-Child Hypoglycemia Confidence Scale PSQI IDSS (T1) SUS INSPIRE-Parent Clarke Questionnaire Human Factors

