12.3.2 Reportable Adverse Events

Adverse events will be assessed on an ongoing basis throughout the study. Adverse event reporting will begin at the start time of the standard therapy phase (i.e., insertion of the CGM sensor) and continue through the hybrid closed-loop Phase 2 and 3 until the subject's participation has ended. All reported adverse

events must be followed until resolution, or until the AE has stabilized, or until the study has been completed.

Pre-existing medical conditions or symptoms observed prior to the start time of the standard therapy phase will not be recorded as an AE and should be collected in the subject's medical history. In the event there is a change (i.e., worsening) in the pre-existing medical condition or symptoms after enrollment meeting the criteria of a reportable adverse event, then an AE must be reported.

For this protocol, a reportable adverse event includes any untoward medical occurrence that meets one of the following criteria:

1. An SAE
2. An ADE unless excluded from reporting in Hypoglycemic Events and Hyperglycemic/Ketotic Events sections below
3. An AE occurring in association with a study procedure
4. An AE not related to a study device issue which leads to temporary or permanent discontinuation of the study device
5. An AE that affects the participant's ability to complete any study procedures
6. An AE for which a visit is made to a hospital emergency department
7. Hypoglycemic Events as defined below
8. Hyperglycemia/Ketotic Events as defined

Skin reactions from sensor or pod placement are only reportable if severe and/or required treatment.

For the purpose of this protocol, mild symptoms of hypoglycemia and hyperglycemia (i.e., clinically non-significant) or blood glucose values out of the normal range (whether or not they resulted in delayed meals or correction boluses) will not be reported as AEs unless determined to meet the reportable criteria in the Hypoglycemic Events and Hyperglycemic/Ketotic Events sections below.

All reportable AEs—whether volunteered by the participant, discovered by study personnel during questioning, or detected through physical examination, laboratory test, or other means—will be reported on an AE eCRF.

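### Protocol 9.7 makes adverse-event assessment at Visit 9 conditional on an in-person visit, contradicting Table 1, its footnote e and section 12.3.2

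*Protocol*

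**What the plan says.** Protocol 9.7 sets the mode and date: "Visit 9 will be conducted either over the telephone or in person at the clinical study site on Study Day 38 ± 3-days". In its list of procedures, vital signs appear with no condition. The next line is the AE assessment, and that line carries the condition: "Assessment of AEs since last visit (if visit is conducted in person at the clinical site".

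The other provisions that govern the same visit are these:

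- **Table 1** (Schedule of Assessments for Phase 1 and Phase 2) marks the AE row at Visit 9, as at the other Phase 2 visits.
- **Table 1, footnote e** lists what a telephone visit may leave out: "Vital signs, device uploads/data review from the BG and Ketone meter are not required at any visit conducted via telephone". AEs are not on that list.
- **Section 12.3.2** states the general rule: "Adverse events will be assessed on an ongoing basis throughout the study".
- **Section 9 (introduction)** says that Phase 2 follow-up visits are to follow Table 1.
- **Section 9.8**, which covers Visits 10 to 12, gives the look-back at the next visit: "Assessment of AEs since last visit".

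**The concern.** Section 9.7 is the instruction a coordinator works from on the day. Read literally, it drops the AE question when Visit 9 is held by telephone. Visit 10 then asks only about the time since the previous visit, so the interval from Visit 8 to Visit 9 may never be asked about.

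Two features make this worth correcting. First, footnote e also waives meter uploads at a telephone visit, and section 12.3.4 defines prolonged hyperglycemia, a reportable AE, by meter glucose and ketone values. At a telephone Visit 9 under 9.7, neither the upload nor the question would be required. Second, person-time keeps accruing whether or not anyone asks. Any event missed this way lowers the reported rate or count, and differences in how sites read 9.7 would make ascertainment vary by site and visit mode.

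**Working it through.** No sample size, power or alpha is involved, and the plan gives no figure to reproduce. The check is a comparison of text, followed by date arithmetic.

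**1. Visits side by side (Protocol 9.2 to 9.9)**

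| Visit | AE assessment | Vital signs |
|---|---|---|
| 4 (in person only) | no condition | not listed |
| 5, 6, 8, 10, 11, 12 | no condition | not listed |
| 7 | no condition | in person only |
| 9 | **in person only** | **no condition** |
| 13 | no condition | in person only |

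Visit 9 is the only visit with a mode condition on AEs. At the two other visits that list vital signs, the condition sits on vital signs, the line directly above the AE line. Visit 9 therefore departs from footnote e twice: it adds a condition on AEs that the footnote does not allow, and it omits the one on vital signs that the footnote does allow. The pattern is that of a parenthetical placed one line too low.

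The AE row in Table 1 carries a superscript, which reads as d (overlapping visit windows) in the text available and may be a misread g (document changes only). Neither footnote makes AE assessment depend on visit mode.

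**2. Length of the interval**

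Inputs: Visit 8 on Day 24, Visit 9 on Day 38, Visit 10 on Day 52, each with a window of 3 days either side (9.6 to 9.8).

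- Visit 8 to Visit 9: 38 − 24 = 14 days. Within the windows, the shortest is (38 − 3) − (24 + 3) = 8 and the longest is (38 + 3) − (24 − 3) = 20.
- Visit 8 to Visit 10: 52 − 24 = 28 days. The shortest is (52 − 3) − (24 + 3) = 22 and the longest is (52 + 3) − (24 − 3) = 34.

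If Visit 10 looks back only to Visit 9, 14 days go unasked. If it looks back to Visit 8, no days are lost, but the recall period is 28 days instead of 14.

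**3. Share of Phase 2 per affected subject**

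Phase 2 runs from Day 1 to Day 94: 94 − 1 = 93 days. The share is 14 / 93 = 15.1%, with a range of 8 / 93 = 8.6% to 20 / 93 = 21.5%.

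**4. Share of study person-time**

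Take 60 evaluable subjects (5.2) and 30.4375 days per month. Total Phase 2 person-time is 60 × 93 / 30.4375 = 183.3 person-months. The share of Visit 9s held by telephone is not stated, so it is an assumption:

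| Telephone share | Person-months without scheduled AE questioning |
|---|---|
| 0% | 0 |
| 25% | 60 × 0.25 × 14 / 30.4375 = 6.9 |
| 50% | 13.8 |
| 100% | 27.6 |

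With 80 subjects the ceiling is 36.8 of 244.4 person-months, which is the same 15%.

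**5. Scale for severe hypoglycemia and DKA**

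Table 5 gives the share of subjects under 18 with at least one event as 4–5% for severe hypoglycemia and 3–4% for DKA. The table does not state a time base; assume one year. The ceiling of 27.6 person-months is 27.6 / 12 = 2.3 person-years. Then 2.3 × 0.04 to 0.05 is about 0.09 to 0.12 subjects with severe hypoglycemia, and 2.3 × 0.03 to 0.04 is about 0.07 to 0.09 with DKA. These are events expected to occur in the interval, not events expected to be missed.

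**6. After correction**

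If AEs are assessed at Visit 9 in either mode, the unasked interval is 0 days and the longest nominal interval between AE assessments from Visit 7 to Visit 13 is 14 days.

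**The case against.** The strongest reply is that the rest of the protocol already covers this. Section 9 sends sites to Table 1, Table 1 marks AEs at Visit 9, footnote e does not waive them, and 12.3.2 sets a continuing duty and accepts events that are volunteered or found by other means. Caregivers have 24-hour contact with the site (9.10). A telephone Visit 9 still includes concomitant medications, device complaints, review of Automated Mode data and the activity and carbohydrate interview, so events can surface. To skip the question, a site would have to follow one line against three other provisions.

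That stands as a limit on the consequence. It does not remove the contradiction: the documents give no rule that ranks Table 1 above the visit text, and 9.7 is an operative instruction.

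A reader might go further and infer that the study's success criterion is biased in favour of the device. The documents do not support that. Success rests on Phase 2 rates of severe hypoglycemia and DKA (Protocol 13.2, SAP 2.4). By definition, the first requires another person's active help for altered consciousness (12.3.3) and the second requires treatment in a health care facility (12.3.4). Both are handled as serious AEs, and one episode of either ends device use for that participant (12.7.1). These are the events least dependent on one scheduled question.

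A reader might also take the two-week gap as certain. It needs three things together: a telephone Visit 9, a site that follows 9.7 over Table 1, and a Visit 10 look-back that stops at Visit 9.

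**Conclusion.** The contradiction is real and plain on the text. It is an internal inconsistency, most likely an editorial slip, and nothing in the documents suggests a deliberate design choice.

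Its size is conditional. Where 9.7 is followed literally at a telephone visit, about 15% of that subject's Phase 2 time has no scheduled AE questioning, or recall lengthens to about 28 days. The 28 of 183 person-months is a ceiling that assumes every Visit 9 is by telephone, every site follows 9.7, and no Visit 10 looks further back. It measures time without a scheduled question, not lost events. Any under-ascertainment would fall mainly on milder reportable AEs in the safety summaries (Protocol 13.6.1, SAP 5.4), and much less on severe hypoglycemia and DKA. No effectiveness figure is affected.

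**What to change.** In Protocol 9.7, move the in-person parenthetical from the AE line to the vital-signs line. AEs are then assessed at Visit 9 in either mode, as Table 1 and 12.3.2 require, and vital signs follow footnote e and match Visits 7 and 13.

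The cost is a one-line protocol correction. It asks nothing of sites beyond what Table 1 already requires, and the SAP needs no change.

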9.9 Visit 13 (End of Phase 2)

Visit 13 will be conducted either over the telephone or in person at the clinical study site on Study Day 94 ± 3 days. This visit will include:

- A1C (blood draw sent to NGSP laboratory)
- Review of concomitant medications
- Height (if visit is conducted in person at the clinical site)
- Weight (if visit is conducted in person at the clinical site)
- Assessment of vital signs (if visit is conducted in person at the clinical site)
- Assessment of AEs since last visit
- Completion of questionnaires (See Table 2: Questionnaires for specific requirements by age group):
 - WHO-5
 - DTSQc Parent
 - P-PAID-Child
 - Hypoglycemia Confidence Scale
 - PSQI
 - IDSS (T1)
 - SUS
 - INSPIRE-Parent
 - Used to measure a caregiver's experience of the support they receive
 - Clarke Questionnaire
 - Human Factors (HF) Questionnaire
 - Measures trust in the Horizon System
- Discontinuation of Horizon Data Portal monitoring if not continuing into Phase 3
- Return study devices if not continuing into Phase 3 (Omnipod Horizon™ System, CGM, BG and ketone meters) if not participating in the extension phase
- Complaints/device deficiencies such as occlusion alarms and system hazard alarms since last visit
- Device uploads for BG and ketone meter
- Data review of Automated Mode use by clinician
- Assessment of activity and routine carb consumption

This visit will mark the discontinuation of Phase 2 and mark the end of the study for subjects not continuing to Phase 3.

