6.3.1 Secondary Endpoints

The secondary objective will be evaluated using the following per subject endpoints *with* prespecified hypotheses:

- Glucose metrics from system CGM during the hybrid closed-loop phase for Phase 2 will be compared to Phase 1 overall:
 - % of time > 180 mg/dL
 - % of time < 70 mg/dL

Additional per subject secondary endpoints *without* prespecified hypotheses used to evaluate the secondary objective include:

- A1C:
 - A1C at the end of Phase 2 (Visit 13), at 6 months (Visit 16), and at the end of Phase 3 (Visit 23; approximately 15 months)

- Change from baseline in A1C at the end of Phase 2 (Visit 13), at 6 months (Visit 16), and at the end of Phase 3 (Visit 23; approximately 15 months)
- Proportion of subjects demonstrating an improvement from baseline in A1C at the end of Phase 2 (Visit 13), at 6 months (Visit 16), and at the end of Phase 3 (Visit 23; approximately 15 months)
- Glucose metrics from system CGM during the hybrid closed-loop phase during Phase 2, and separately during Phase 3 will be compared to Phase 1 during the day, overnight, and overall:
 - Mean glucose
 - % of time in range 70-180 mg/dL
 - % of time in range 70-140 mg/dL
 - % of time > 180 mg/dL
 - % of time \geq 250 mg/dL
 - % of time \geq 300 mg/dL
 - % of time < 70 mg/dL
 - % of time < 54 mg/dL
 - Standard deviation
 - Coefficient of variation
- Percentage of time in hybrid closed-loop as proportion of overall device usage time during Phase 2, and separately during Phase 3
- Glucose management indicator (GMI) based on overall mean glucose during Phase 2 and, separately during Phase 3 will be compared to Phase 1
- Insulin requirements during Phase 2 and, separately during Phase 3 will be compared to Phase 1:
 - Total daily insulin (TDI) (units, units/kg)
 - Total daily basal insulin (units, units/kg)
 - Total daily bolus insulin (units, units/kg)
- Change from baseline in BMI (kg/m²) at end of Phase 2, and at the end of Phase 3

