Subjects will have scheduled follow-up visits according to Table 1: Schedule of Assessments for Phase 1 and Phase 2 and complete questionnaires according to Table 2: Questionnaires. Visits will be conducted either in person at the clinical study site or over the telephone or videoconference. Subjects and/or parents/guardians may also choose to use email or text as a substitute for their scheduled telephone visit. In the event of overlapping visit windows, no visits occurring during Phase 2 are to occur on the same date.

The duration of the hybrid closed-loop phase for Phase 2 will last ~13-weeks.

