9.11 Early Withdrawal (Phase 2)

Any subject may withdraw early from the study at any time for any reason. Upon withdrawal, subjects will be asked to complete the assessments according to Table 1: Schedule of Assessments for Phase 1 and Phase 2. The investigator may also terminate a subject's participation in the study if it is in the best interest of the subject or if the Sponsor or local regulatory agency (e.g., FDA) terminates the study.

The Early Withdrawal visit will include:

- A1C (blood draw sent to NGSP laboratory)
- Review of concomitant medications
- Height
- Weight
- Assessment of vital signs
- Assessment of AEs since last visit
- Completion of questionnaires (see Table 2: Questionnaires for specific requirements by age group):
 - WHO-5
 - DTSQc Parent
 - P-PAID-Child
 - Hypoglycemia Confidence Scale
 - PSQI
 - IDSS (T1)
 - SUS
 - INSPIRE-Parent

- Used to measure a caregiver's experience of the support they receive
- Clarke Questionnaire
- Human Factors (HF) Questionnaire
 - Measures trust in the Horizon System
- Discontinuation of Horizon Data Portal monitoring
- Return all study devices
- Complaints/device deficiencies such as occlusion alarms and system hazard alarms since last visit
- Device uploads for BG and ketone meter
- Data review by clinician
- Assessment of activity and routine carb consumption

The reason for withdrawal will be recorded, and their participation in the study will end.

In the event of a subject's death during the study, the subject's participation will be considered terminated and the date of death will be used as the date of study exit.

10 HYBRID CLOSED-LOOP – PHASE 3

The hybrid closed-loop Phase 3 extension will commence at **Visit 13** upon conclusion of hybrid closed-loop Phase 2 and after all assessments are performed according to Table 1: Schedule of Assessments for Phase 1 and Phase 2. Phase 3 assessments are to be performed according to Table 3: Schedule of Assessments for Phase 3

For subjects that do not extend their participation into the extension phase, the reason for study exit at Visit 13 will be documented. This will not be considered an early withdrawal from the study.

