7.5 HANDLING OF MISSING DATA

All practical monitoring and follow-up steps will be taken to ensure complete and accurate data collection. All analyses will be based on available data only; no imputation for missing data is planned.

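### Section 9.9 drops height and weight at a remote Visit 13, Table 1 does not, and the end-of-Phase-2 BMI change may be missing for those children

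*Protocol*

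**What the plan says.** - **Visit mode.** Protocol 9.9: "Visit 13 will be conducted either over the telephone or in person at the clinical study site on Study Day 94" (± 3 days). Table 1 marks the visit as telephone or office. Section 9 adds that families "may also choose to use email or text as a substitute for their scheduled telephone visit", and makes no exception for Visit 13.
- **Measurements in 9.9.** "Height (if visit is conducted in person at the clinical site" and "Weight (if visit is conducted in person at the clinical site". The A1C blood draw in the same list carries no such condition.
- **Measurements in Table 1.** Height and weight have their own rows, separate from vital signs, and are scheduled at screening, Visit 13 and Early Withdrawal. Footnote e gives the telephone waiver: "Vital signs, device uploads/data review from the BG and Ketone meter are not required at any visit conducted via telephone". Height and weight are not in it.
- **Entry to Phase 3.** Protocol section 10 has the extension begin at Visit 13 "after all assessments are performed according to Table 1: Schedule of Assessments for Phase 1 and Phase 2".
- **Endpoint.** Protocol 6.3.1 lists "Change from baseline in BMI (kg/m²) at end of Phase 2, and at the end of Phase 3" among the secondary endpoints without prespecified hypotheses. SAP 3.3 lists the same endpoint.
- **Analysis.** SAP 6.6 uses Visit 13 data for parameters measured at the end of Phase 2. SAP 7.5: "All analyses will be based on available data only; no imputation for missing data is planned".

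**The concern.** Two parts of the protocol give sites different instructions for the same visit. Under 9.9 a site can hold Visit 13 remotely, take no height or weight, and regard the visit as complete. Under Table 1 and section 10 the same visit is incomplete. The looser instruction removes the only scheduled measurement from which the end-of-Phase-2 BMI change can be computed for a child who completes the phase.

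What is at stake is one named secondary endpoint. With no imputation, it would be summarized over children whose families came to the site. That group is self-selected, and its size cannot be foreseen from the documents.

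**Working it through.** The plan states no figure on this point that could be reproduced, so the check is mainly a comparison of passages.

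**1. Is there a contradiction?**

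| Item at a telephone Visit 13 | Table 1 with footnote e | Section 9.9 |
|---|---|---|
| A1C blood draw | required | required |
| Vital signs | waived | only if in person |
| Height | required | only if in person |
| Weight | required | only if in person |

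The two sources agree on A1C and vital signs and disagree on height and weight. Because Table 1 lists these apart from vital signs, the vital-signs waiver cannot be read to cover them.

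**2. Does another scheduled visit supply the value?** Sections 9.2 to 9.8 (Visits 4 to 12) list no height or weight. Section 9.10 leaves extra assessments at unscheduled visits to the investigator. Early Withdrawal (9.11) includes both measurements and is an office visit, but it does not apply to completers: section 10 says that a child who stops at Visit 13 is not an early withdrawal. The exploratory BMI analysis at last follow-up (protocol 6.4, SAP 7.6) has no other scheduled Phase 2 measurement to draw on.

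**3. Does the analysis plan fill the gap?** No. SAP 6.6 names Visit 13 as the source, and SAP 7.5 rules out imputation.

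**4. How large could the gap be?** Let N be the number of children and f the share with a remote Visit 13 who are not measured otherwise. N = 60 is the evaluable target (protocol 5.2, SAP 2.1). The documents give no f, so the values below are assumptions.

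- Missing = N × f
- Width of the confidence interval for the mean BMI change, relative to complete data = 1/√(1 − f), if the standard deviation is unchanged

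| f (assumed) | Missing of 60 | Left | Relative CI width |
|---|---|---|---|
| 10% | 60 × 0.10 = 6 | 54 | 1/√0.90 = 1.05 |
| 25% | 60 × 0.25 = 15 | 45 | 1/√0.75 = 1.15 |
| 50% | 60 × 0.50 = 30 | 30 | 1/√0.50 = 1.41 |

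If all 80 children who may be enrolled reached Visit 13, the missing counts would be 8, 20 and 40, with the same relative widths. The loss of precision is modest unless f is large. Any selection effect cannot be sized from the documents.

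**The case against.** The strongest case against the point is that it is minor. BMI change is one of many secondary endpoints without a hypothesis. SAP 6.6 says that results in this group will not support clinical claims, and study success rests on severe hypoglycemia and DKA (SAP 2.4). Section 9.9 stops requiring the measurement at a remote visit but does not forbid it, so a child could be measured when blood is drawn. Nothing shows that attendance is related to BMI. The contradiction could also be closed by adding height and weight to footnote e. All of this is fair. It makes the accurate claim that the value may be missing, not that it will be, and it keeps the point small. It does not remove the conflict, and widening footnote e would settle the wording while leaving the endpoint exposed.

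A reader might also infer more than the documents support:

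- **That the A1C endpoint is at risk.** Section 9.9 lists the draw without an in-person condition, and footnote e does not waive it.
- **That losing meter uploads matters to the results.** Time in range is computed from CGM readings (SAP 7.4). Meter data feed no primary or hypothesis-tested endpoint.
- **That Phase 2 insulin per kg must use the screening weight.** SAP 6.4 does not say which weight is the divisor for any child.
- **That Visit 23 has the same defect.** Section 10.9 permits a telephone visit but lists height and weight unconditionally, and footnote l of Table 3 waives only meter uploads.
- **That a text message could be the whole of Visit 13.** Section 9 lets it replace the telephone contact, but 9.9 still lists a blood draw and questionnaires.

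**Conclusion.** The point holds as a conflict between section 9.9 and Table 1 with a limited consequence. If sites follow 9.9 as written, the end-of-Phase-2 BMI change may be missing for children with a remote Visit 13, leaving a self-selected group seen in person. The possible loss is 6, 15 or 30 of 60 children at assumed remote rates of 10%, 25% or 50%, provided that those children are not measured at another contact. The endpoint is descriptive. Neither the two primary effectiveness endpoints nor the two secondary endpoints with hypotheses depend on it.

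The text does not require Visit 13 to become an office-only visit. That would be a trade-off against flexibility that the protocol allows, and the gap can be closed without it.

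**What to change.** - In section 9.9, delete the in-person condition on height and weight so that it agrees with Table 1. Require both to be measured within day 94 ± 3, at the contact where the A1C blood is drawn.
- In section 9, state that email or text alone does not complete Visit 13.
- In the SAP, state that the number of children with a measured end-of-Phase-2 BMI will be reported beside the summary.

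The cost is a few lines of protocol and SAP text and slightly less flexibility for families at one visit. The blood-draw contact has to take place anyway. The documents do not say where blood is drawn from children seen remotely, so the sponsor should confirm that height and weight can be measured there.
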